**1 PROTOCOL SUMMARY****1.1 SYNOPSIS**

Title:	Implementing Prescriber-Pharmacist Collaborative Care for Evidence-based Anticoagulant Use	
Study Description:	
Direct oral anticoagulant medications are commonly used to treat or prevent thrombotic conditions, such as pulmonary embolism, deep vein thrombosis, and atrial fibrillation. However, up to 10-15% of patients receiving these medications get unsafe doses based on a patient's kidney or liver function, potential interactions with other medications, and indication for taking the medication. Medication alerts and notifications directed to prescribers may be beneficial for improving evidence-based prescribing, but can be burdensome. This study will improve upon the existing systems by testing augmentations that encourage collaboration between prescribing health care providers (e.g., physicians, nurse practitioners) and expert pharmacists working in anticoagulation clinics and incorporating dynamic long-term monitoring of patient needs, as well as updates to evidence-based guidelines. The target participant for this trial is the DOAC prescriber (physician, physician assistant, nurse practitioners). We will specifically test two different clinical situations: (1) a medication alert at the time an inappropriate new direct oral anticoagulation (DOAC) prescription is written, and (2) a medication notification that is sent anytime a new prescribing error develops after the initial DOAC prescription is written. This project will implement and evaluate an Electronic Health Record (EHR) medication alert and notification system to improve safe DOAC prescribing through prescriber-pharmacist collaboration. Findings from this project will establish a framework for implementing prescriber-pharmacist collaboration for high risk medications, including anticoagulants.
	
Objectives:	Primary Objective:	Implement and evaluate EHR medication alert and notification systems to improve safe DOAC prescribing through prescriber-pharmacist collaboration.
Endpoints:	Primary Endpoint:	The number (proportion) of notifications (in the existing-prescription notification conditions) that are addressed within 7 days.

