**Recommended Actions:**

- Substitute dronedarone with another medication
- Replace rivaroxaban with warfarin
- Replace rivaroxaban with apixaban

**Reason:** Dronedarone is a combined P-g0 and moderate CYP3A4 inhibitor, which can lead to higher levels of rivaroxaban when CrCl < 30 mL/min. This can place the patient at risk for bleeding complications. CrCl is calculated using the [Cockcroft-Gault Equation](#), based on sex, age, weight and serum creatinine.

Relevant Labs and Weight Trend (4/7 available)	11/7/21	8/11/21	6/1/20	9/23/19	More labs over the last 18 months are available
Creatinine	1.6	1.3	1.3	1.3	
Weight (kg)	58	52	52	-	
Creatinine Clearance (mL/min)	34	45	45	45	

\*GFR does not impact recommendation

Call an Anticoagulation pharmacist for assistance by [contact]am-5pm, M-F.

**Response to Recommended Actions** (all feasible drug replacements are shown)

Remove the following orders?

☒ Rivaroxaban (XARELTO) 20 mg tablet  
Take 1 tablet (20 mg) by mouth once daily with dinner. Disp - 30 tablets, R-3, Normal

Apply the following?

☒ Order alternative drug for indication; apixaban (ELIQUIS) 2.5 mg tablet BID

☒ Order alternative drug warfarin 5 mg daily and refer patient to the Anticoagulation Clinic for ongoing monitoring and treatment

☒ Referral to Anticoagulation Pharmacist for final decision and action

Discontinue dronedarone

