**Prescribers change when alerted.** During a recent pilot study that we conducted, when prescribers were contacted about unsafe DOAC use they made meaningful changes in 51/81 (63%) cases. Actions taken included changing the medication, changing the dose, or discontinuing an interacting medication. When changes were not made, a thoughtful discussion usually occurred between the prescriber and an anticoagulation expert focusing on unique patient factors.

**Proposed Intervention.** We propose two different interventions to improve DOAC prescribing. The first intervention is an automated EHR alert that occurs at the time a DOAC medication is prescribed but some potential error exists (e.g., drug-drug interaction, wrong dose for given renal function). Prescribers will be randomized to receive a detailed alert, but half will include a referral link for optional pharmacist review and the other half will receive an alert that does not include the pharmacist review referral link.

The second intervention is an EHR notification that is sent to the inbox of either the DOAC prescriber or an anticoagulation pharmacist anytime *after* a DOAC medication is prescribed when a new potential issue develops (e.g., worsened renal function that impacts dosing, new drug-drug interactions).

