## 3 OBJECTIVES AND ENDPOINTS

OBJECTIVES	ENDPOINTS	JUSTIFICATIONS
Primary		
Determine the effect of notifications regarding existing DOAC prescriptions on prescriber behavior	The number (proportion) of notifications (in the existing-prescription notification conditions) that result in any prescription change within 7 days.	The goal of alerts and notifications is to bring about corrections in prescription errors. Given that “correct” is not always an absolute assessment, our primary outcome measure will capture any change to the DOAC prescription that results from the notification.
Secondary		
Determine the effect of alerts regarding newly prescribed DOACs on prescriber behavior	The number (proportion) of alerts (in the newly prescribed DOAC alert conditions) that result in any prescription change within 7 days.	The goal of alerts and notifications is to bring about corrections in prescription errors. Given that “correct” is not always an absolute assessment, our primary outcome measure will capture any change to the DOAC prescription that results from the notification.
	Change in magnitude of effect for the existing-prescription notification over time. This is reported on at the institution level (not individual level).	The effectiveness of notifications should be sustained over time. This measure examines longitudinal trends in effectiveness.

	(This outcome measure analysis is based on the primary outcome)	
	Change in magnitude of effect for the new-prescription alert over time, reported on at the institution level (not individual level).	The effectiveness of alerts should be sustained over time. This measure examines longitudinal trends in effectiveness.
Tertiary/Exploratory		
Determine the effectiveness of promoting pharmacist-prescriber collaboration in new DOAC prescriptions through the design of CDS alerts	The difference in outcome measures (primary and secondary outcomes) between Notification A and B conditions	While alerts are expected to reduce prescription errors, variations in alert and design to encourage pharmacy collaboration may provide added benefit

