## 8 STUDY ASSESSMENTS AND PROCEDURES

### 8.1 EFFICACY ASSESSMENTS

**Outcome Measurements:**

Our **primary** outcome measure (adoption) is the proportion of DOAC notifications that lead to a change in the prescription within seven days. The denominator is the total number of DOAC prescription notifications that are sent to either the prescriber or pharmacist (per randomization). The numerator is the number of DOAC notifications that result in any change to the DOAC prescription within seven days after the notification has been sent.

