## 9.3 STATISTICAL ANALYSES

### 9.3.1 GENERAL APPROACH

The main effect analyses will allow us to determine the impact of different alert- and notification types on evidence-based DOAC prescribing in both newly prescribed DOAC prescriptions and existing DOAC prescriptions in order to understand under what contexts prescriber-pharmacist collaboration is an effective implementation strategy. In both our primary and secondary outcomes, our analyses will compare the main effects of each intervention, i.e., new prescription alerts (Alerts 1 vs 2) and existing-prescription notifications (Notifications A vs B), to determine which are most effective. For both interventions, the outcome of interest will be whether the patient whose prescription triggered the alert/notification (i.e., is receiving a non-evidence based DOAC) has their prescription changed following the alert or notification.

For the primary intervention outcome (existing-prescription notifications), main effect analyses will compare the proportion of patients receiving an evidence-based DOAC prescription within seven business days following the notification between prescribers randomized to receive the notifications themselves vs. prescribers for whom notifications were sent directly to anticoagulation clinic pharmacists.

For the secondary intervention outcome (new DOAC prescription alerts), main effect analyses will compare the proportion of patients receiving an evidence-based DOAC seven business days following the notification between prescribers randomized to receive enhanced alerts vs. enhanced alerts plus pharmacist referral.

The treatment interaction will allow evaluation of whether certain alerts and notifications work better when provided in tandem.

The main outcome analysis will use mixed-effects logistic regression models to account for the binary patient-level outcome variable of evidence-based DOAC receipt after an alert. The two treatment factors and their interaction will be included as fixed effects, as well as any stratification variables and baseline patient- and/or prescriber-level characteristics that are unbalanced. A prescriber-level random effect will account for patient clustering within prescribers, and an unstructured covariance matrix will be used for residual errors. Similar mixed-effects regression analyses will be conducted for secondary outcomes, adapted for different outcome measures or levels of analysis.

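### The primary endpoint's success criterion is stated in three conflicting ways, and the formal numerator does not say how a response made only through the interacting drug is scored

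*Combined protocol and SAP*

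**What the plan says.** **Addressed.** The synopsis (Section 1.1) gives the primary endpoint as "The number (proportion) of notifications (in the existing-prescription notification conditions) that are addressed within 7 days". No section defines the term.

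**DOAC prescription changed.** Section 8.1 sets the formal numerator: "The numerator is the number of DOAC notifications that result in any change to the DOAC prescription within seven days". Section 9.3.2 analyses the same quantity. In the Section 3 table the endpoint cell is looser, counting notifications "that result in any prescription change within 7 days", but its justification cell restricts this to the DOAC. The reason given there is that correctness cannot always be judged absolutely. The alert numerator in Section 8.1 and the alert analysis in Section 9.3.3 are built the same way.

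**Evidence-based DOAC.** For the same primary comparison, Section 9.3.1 says that "main effect analyses will compare the proportion of patients receiving an evidence-based DOAC prescription within seven business days following the notification". It chooses mixed-effects logistic models to "account for the binary patient-level outcome variable of evidence-based DOAC receipt after an alert". Section 8.2 also calls adoption of evidence-based DOAC prescription the primary outcome measure. Yet the first paragraph of Section 9.3.1 says the outcome of interest is whether the prescription was changed.

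**Interacting drugs.** Section 2.1 lists new drug-drug interactions as a trigger for notifications. Of the pilot's meaningful changes (51 of 81) it says: "Actions taken included changing the medication, changing the dose, or discontinuing an interacting medication". The sample new-prescription alert in Figure 2 lists "Substitute dronedarone with another medication" among its recommended actions.

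**The concern.** An analyst could code either the change variable or the evidence-based variable as the primary outcome and claim to have followed the plan. The two are not interchangeable. Section 3 chooses any change precisely to avoid judging correctness, and the Section 9.3.1 model then depends on that judgement.

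The second difficulty is a gap in scoring. Where a notification is triggered by an interaction and the response is to alter only the interacting drug, the DOAC order stays as it was. Section 8.1, taken at its word, records no event. The arms differ in who acts first, a pharmacist or the prescriber (Section 6.1.1), so the mix of responses could differ by arm. Any loss from the numerator could then bias the comparison as well as dilute it.

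**Working it through.** **Step 1. Set the criteria side by side.**

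| Response to a notification | Addressed (1.1) | DOAC prescription changed (8.1, 9.3.2) | Evidence-based DOAC (8.2, 9.3.1) |
|---|---|---|---|
| DOAC changed to a regimen that meets the guidelines | presumably yes | success | success |
| DOAC changed to another regimen that does not | unclear | success | failure |
| Only the interacting drug changed, after which the DOAC meets the guidelines | presumably yes | not counted | success |
| Reviewed and discussed, nothing changed | unclear | not counted | failure |

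Row 2 is not far-fetched: the examples of inappropriate management in Section 8.4.2.2 are themselves DOAC dose changes. Row 4 matters because Section 2.1 reports that a discussion usually took place when pilot prescribers made no change.

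**Step 2. Reproduce the stated power.** Inputs from Section 9.1: 150 prescribers per arm, 2 patients each, ICC 0.1, alpha 0.05, 40% vs 52%. I assume a two-sided test, which this calculation does not state.

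- Effective n per arm = 150 × 2 / [1 + (2 − 1) × 0.1] = 300 / 1.1 = 272.7.
- Power = Φ{ [|p1 − p2| − 1.96 √(2 p̄(1 − p̄)/n)] / √([p1(1 − p1) + p2(1 − p2)]/n) }.
- With p̄ = 0.46, the two roots are 0.0427 and 0.0424. Then (0.12 − 1.96 × 0.0427) / 0.0424 ≈ 0.86, and power = 80.5%.
- In reverse, 270 effective patients per arm are needed, and 270 × 1.1 × 2 = 594, against 600 planned.

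The 80% in the text reproduces, so the point concerns the outcome definition and not this arithmetic. (Table 3 shows 63% for the same scenario, base 0.4 and risk ratio 1.3 with 2 patients. That mismatch is a separate matter.)

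**Step 3. Illustrate the interacting-drug gap.** Let s be the share of responses made only through the interacting drug and so left out of the Section 8.1 numerator. The documents give no value for s, so the range is an assumption. The observed rate is p(1 − s). The calculation also supposes that the starting rates include such responses, which Section 9.1 does not say.

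Equal s in both arms:

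| s | From 40% vs 52% | Power | From 40% vs 60% | Power |
|---|---|---|---|---|
| 0 | 40.0% vs 52.0% | 80% | 40.0% vs 60.0% | 99.7% |
| 10% | 36.0% vs 46.8% | 73% | 36.0% vs 54.0% | 99% |
| 20% | 32.0% vs 41.6% | 64% | 32.0% vs 48.0% | 97% |
| 30% | 28.0% vs 36.4% | 56% | 28.0% vs 42.0% | 93% |

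Unequal s, from 40% (prescriber arm) vs 52% (pharmacist arm):

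- s = 10% and 30%: 0.40 × 0.9 = 36.0% vs 0.52 × 0.7 = 36.4%. The difference all but vanishes.
- s = 30% and 10%: 0.40 × 0.7 = 28.0% vs 0.52 × 0.9 = 46.8%. The difference grows from 12 to 18.8 percentage points.

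**The case against.** The strongest reply is that the intended endpoint can be identified. Sections 3, 8.1 and 9.3.2 agree on a change to the DOAC prescription, Section 3 gives a reason, and Section 9.3.1 itself says once that the outcome is a changed prescription. On this view the evidence-based wording is loose drafting. This has weight: the three criteria do not have equal support. But Section 9.3.1 is where the model is specified, and it names evidence-based receipt as the outcome variable. Section 8.2 attaches the words primary outcome to the same thing. Blinding the team during analysis (Section 6.3) limits opportunistic choice but does not say which variable to code.

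Four stronger readings are tempting and are not supported.

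- A reader might infer that the 40% and 60% planning rates counted interacting-drug changes, as the pilot in Section 2.1 did. Section 9.1 cites only pilot data on changed prescriptions, and Section 2.1 reports 63% overall with no split by pharmacist involvement. Nothing links the two. If the planning rates already counted DOAC changes only, the power losses in Step 3 do not arise.
- A reader might conclude that the gap would erase the treatment effect. Only one assumed split does that. The reverse split inflates the effect, and nothing in the documents favours either.
- A reader might take a loss of 20 to 30% as likely. Section 2.1 describes causes other than drug interactions as more common, and the share is not given.
- A reader might treat the Figure 2 action on the interacting drug as a notification response. It comes from a sample alert, and the sample notification recommends a DOAC dose change, which Section 8.1 does count. For notifications the support is the trigger list and the pilot sentence in Section 2.1. The alert example bears directly only on the secondary outcome.

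Section 8.2 also measures time to a DOAC change or related documentation, and how often the recommended drug is ordered. These give supporting data but do not repair the primary numerator.

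**Conclusion.** The point holds. The primary outcome variable is not uniquely defined, and the competing criteria score the same response differently. That conclusion rests on the text alone and needs no assumption.

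That interacting-drug responses go uncounted follows from a literal reading of Section 8.1. No section says so outright, and none says otherwise. The size and direction of the consequence are unknown. Under assumed equal losses of 10 to 30%, power ranges from 73% down to 56% at the minimum detectable difference, and stays at 93% or above at the pilot rates. Unequal losses could bias the comparison either way. The figures show that the scoring rule can matter; they do not estimate how much it will.

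**What to change.** - State one numerator in Sections 1.1, 3, 8.1, 8.2, 9.3.1, 9.3.2 and 9.3.3. Suggested scoring rule: any change to the DOAC order, or to the order for the interacting drug named in the notification or alert, within the window. Either drop the word addressed or define it as this.
- Make the model outcome in Section 9.3.1 the same variable.
- Keep evidence-based DOAC receipt as a named secondary outcome. Define it separately for alerts, which fire at ordering, and for notifications, which come from the daily registry.
- Say in Section 9.1 which responses the 40% and 60% planning rates counted.
- While editing, settle the window, which is 7 days in some places and seven business days in others.

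The cost is wording plus one more order field in the EHR extract. Section 10.1.7.1 already lists concomitant medications among the stored data. The change should be made before the outcome is coded. It concerns scoring only and does not judge which clinical response is right.

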**Secondary**

Our **secondary** outcome measure (adoption) is the proportion of DOAC alerts that lead to a change in the prescription within seven days. The denominator is the total number of DOAC prescription alerts with or without a visible option for pharmacist consultation (per randomization). The numerator is the number of DOAC alerts that result in any change to the DOAC prescription within seven days after the alert has occurred.

**Effectiveness:** We will evaluate the effectiveness of our DOAC alert system components by examining patient level 30-day clinical adverse event rates (bleeding and thrombotic). This time period was selected to minimize potential contamination from the safety review mechanism described above, and we recognize that rates for the adverse events will be low. Supplementary analyses will also examine the effect of the alert system overall on adverse events.

Clinical adverse events assessed will include major and clinically-relevant non-major bleeding (CRNMB) events, as defined by the International Society on Thrombosis and Haemostasis (ISTH), new or recurrent VTE events, and stroke or systemic arterial embolic events. Each of these events will be captured using health informatics tools (described below) and independently adjudicated by two expert clinicians (one pharmacist, one prescriber) who meet once in Y1 and twice in Y2 to adjudicate any potential adverse events. We will use two Michigan Medicine-developed health informatics tools, DataDirect and EMERSE, to identify adverse events and capture clinical data (e.g., notes, labs, imaging, procedure reports) for adjudication. These tools allow for rapid identification of populations based on granular clinical details (e.g., demographics, diagnosis, medication use) and for textbased searches of the medical record for key terms (e.g., “bleeding”, “stroke”) across pre-defined patient populations. The adjudicators will be blinded as to which alert the patient’s prescribing clinician was randomized. Using these EHR search tools, we can also capture all ICD10 diagnosis and procedure codes for longitudinal system-level analyses. [See Appendix A for current list of ICD10 codes used.]

**8.2 IMPLEMENTATION OUTCOMES**

Our exploratory analysis of outcomes will follow the RE-AIM implementation evaluation framework.

**Reach:** All alerts for unsafe DOAC use will be categorized based on the prescriber specialty and patient characteristics (e.g., demographics, comorbidities). These will be described both independently for the both the alerts and the notifications separately, as well as in aggregate. We will also examine the proportion of patients on DOACs that had alerts or notifications fire, as well as the proportion of prescribers that received alerts and/or notifications. Finally, we will examine the frequency of unsafe DOAC prescribing for prescribers who opt out of the alert system.

**Adoption:** In addition to our primary outcome measure of prescriber-level adoption of evidence-based DOAC prescription, secondary adoption measures will examine the frequency and clinical predictors of prescribers who dismiss the new-prescription alert or ignore the existing-prescription notification (defined as no action within seven calendar days). We will also identify the frequency and predictors of prescribers who use anticoagulation clinic pharmacist referrals in new-prescription alerts.

**Implementation** (including fidelity): To address how various EHR alerts impact implementation of evidence-based DOAC prescribing, we examine process measures related to prescriber and pharmacist alert and notification receipt.

For prescribers, we will examine how often they order (or do not order) the recommended medication (and whether they provide a reason when they do not order) for both new-prescription alerts and existing prescription notifications. For pharmacists, we will measure how often they respond to referrals at the time of initial prescribing or to existing-prescription notifications, as well as the time from referral/alert until the pharmacist documents a recommendation in the EHR. For existing-prescription notifications, we also will measure the time from notification until the notification is read as well as time until any DOAC prescription change or related EHR documentation occurs (automated chart abstraction using EMERSE, validated by random manual chart review) as well as the number of times a existing-prescription notification is read before being acted on.

**Maintenance:** To measure maintenance and sustainment, we will assess all “reach” and “adoption” outcomes after 6 and 12 months for all patients, and after 18 months for the subset of prescribers enrolled prior to the second quarter of Year 2. This will also allow us to investigate whether treatment effects for prescribers are maintained after the initial adoption.

